4. Adverse events: Events within the list of Rare and Iatrogenic Adverse Reactions (RAIDAR) compiled by the DSRU (Annex 1) will be automatically followed up if a more likely alternative explanation for their occurrence is not given.

#### 9.3.5 Methods to Maximise Questionnaire Response Rate

Patient 12 week end of observation questionnaire

A proportion of Specialist HCPs or GPs are likely to fail to submit these questionnaires. Methods to maximise response rates will include prompts from study facilitators by phone, email and personal contact and reminder questionnaires targeted at those who have not responded within one month of the date the initial questionnaire was sent.

#### Specific event follow-up questionnaires

A duplicate event follow-up questionnaire will be sent to specialist HCPs or GPs for the specific patient(s) for whom they have not responded to the initial follow-up questionnaire; within six weeks of the date the initial event follow-up questionnaire was sent. Specialist HCPs and GPs will be offered remuneration for each follow-up questionnaire that is completed and returned to the DSRU.

#### 9.4 Data Sources

Medical chart based data collection in this study will be conducted in various phases; relevant documentation (such as information leaflets, questionnaire, consent forms, etc) will be available both as hard copies and electronically for download by the participating specialist HCPs.

#### 9.4.1 Recruitment

This first phase will have two parts.

#### Part 1: Recruitment of eligible specialist HCPs.

The DSRU will allocate a unique study reference number to each participating specialist HCP for study audit and data management processes.

#### Part 2: Recruitment of eligible patients initiated with the study drug combination under clinical care of participating specialist HCPs.

For all eligible consented patients invited to participate, the specialist HCP or a member of their clinical team, will be asked to record anonymously (using the study reference number provided on patient study documentation) a summary of non-clinical reasons for prescribing, demography (age and sex), indication and selected treatment details onto a simple questionnaire and submit these data to the DSRU coordinating centre either through a secure online website, or via surface mail. Date of recruitment into the study Version 7 Date: 30/08/2017

will also be recorded by the specialist HCP, if known, or, retrospectively once the consent form is obtained, by the DSRU research staff. The unique study reference number allocated to each patient will be used for study audit and data management processes.

#### 9.4.2 Exposure and outcome data

This second phase will also have two parts.

#### Part 1: Covariate data

Thirteen weeks post antiplatelet therapy start date, the specialist HCP will be prompted to complete a second questionnaire which will gather information on medical history and medication use prior to or present on start date; changes on general health and medications during treatment and clinical events of medical interest. For some patients, the patient's GP will also be contacted to complete an abridged end of survey questionnaire. This will depend on the care pathway and whether the specialist HCP will have any further contact with the patient after discharge to primary care.

#### Part 2. Follow-up.

Events of interest will be collectively evaluated to inform on clinical features that may be important when considering drug-relatedness; this requires follow-up using event-specific questionnaires sent to the specialist HCP (see 9.3.4) or GP depending on reporter. With the exception of these enquiries for additional information on selected events, no further monitoring of patients for purposes of data collection will occur post the survey period.

#### 9.5 Study Size

The ability to detect an adverse event is dependent on the expected incidence rate of the adverse event in those exposed to the drug, the background rate in those not exposed to the drug, and the total number of patients.

Where studies, such as clinical trials, have already estimated the impact of the exposure on the outcome of interest, the objective should be to estimate the magnitude of the effect as precisely as possible (21). As such, in this study it is more appropriate to choose a sample size that will yield a confidence interval of a predefined width for those identified risks defined within the primary outcome which are of greatest clinical and medical importance i.e. major bleeding outcomes. Table 4 displays the samples sizes (95% confidence intervals) across a range of expected incidences and levels of precision. From rivaroxaban clinical trial data, the cumulative incidence risk of first occurrence of adjudicated major bleeding events (intracranial, GI and urogenital) in patients taking rivaroxaban for secondary prevention after ACS over the first 12 weeks of treatment was approximately 0.5% (0.1%, 0.3% and 0.1%). Thus in this population of patients with ACS treated with rivaroxaban, in order to estimate the expected (true) cumulative incidence of primary outcomes of major bleeding events of 0.5% within +/- 0.4%, we would ideally need a sample size of 1193 patients (Table 4). An equivalent number of patients within the contextual comparator cohort is desirable.

Incidence									
from RCT	Precision								
(%)	0.2%	0.3%	0.4%	0.5%	0.6%	1%	2%	3%	5%
0.10	958	426	240	153	107	38	10	4	2
0.20	1913	851	479	307	213	77	19	9	3
0.30	2864	1275	718	459	319	115	29	13	5
0.40	3812	1698	956	612	425	153	38	17	6
0.50	4755	2119	1193	764	531	191	48	21	8
0.70	6631	2958	1666	1067	741	267	67	30	11
0.80	7564	3376	1902	1218	846	305	76	34	12
1.00	9418	4208	2371	1519	1055	380	95	42	15
1.25	11716	5241	2955	1893	1315	474	119	53	19
1.50	13991	6267	3535	2265	1574	567	142	63	23
2.00	18475	8296	4684	3003	2087	752	188	84	30
3.00	27187	12268	6938	4452	3096	1117	279	124	45
4.00	35566	16126	9135	5866	4081	1473	369	164	59
5.00	43627	19871	11276	7246	5043	1821	456	203	73

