## 5 Amendments and Updates

### 6 Milestones

Planned date	
18th September	
2015	

End of data collection	18th September
Interim report 1	2018 1st November
Final report of study results	2017 August 2019
Final report of study results	August 2019

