Study start is defined as the date that the first patient is recruited into the study (18th September 2015), and continue for a maximum of 36 months, or until the target sample size (1193 tbc) for both cohorts has been achieved (whichever is the soonest). The final cohort sizes, period of observation and the duration of the SCEM study will be dependent on the level of prescribing of rivaroxaban in combination with standard oral antiplatelet therapy by specialist HCPs in England and Wales. Data collected during later calendar time periods can be compared with earlier periods to identify any trends that may emerge. Slow uptake may impact on the ability to meet the study objectives; in this instance, further discussions with the regulatory authorities regarding study feasibility will be needed.

Patients will be observed from the date antiplatelet therapy was prescribed as part of the acute management of the ACS in both the rivaroxaban group and the contextual Version 7 Date: 30/08/2017

cohort for 13 weeks in order to allow for detection of outcomes associated with treatment initiation (this will allow for a delay between antiplatelet therapy administration as part of the acute treatment for the ACS, and the subsequent start of rivaroxaban to ensure 12 complete weeks of observation time for analysis). The index date for analysis for both groups will be defined dependent on the prescribing patterns observed in real life use. Since patient care is likely to be shared between secondary and primary care for most patients during the observation period, the patient's GP will be contacted at least 13 weeks after antiplatelet therapy start date to complete an abridged questionnaire to collect any information on outcomes of interest that they are aware of during the observation period to minimise under-reporting on selected outcomes. For the main statistical analysis, events will be censored at 12 weeks post index date, should they be reported after this time period. However, events of interest will be included and detailed in study reports even if they occurred after the 12 week time period. Where additional outcomes are identified that have not be reported by the initiating prescriber, these will be followed-up with the GP to ascertain further information.

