#### 9.2.5 Evaluable cohort

Evaluable patients are those patients who have provided consent and for whom analysable clinical data has been provided in the data collection questionnaires. Evaluable patients for whom the 12 week survey questionnaire (from both specialist HCP and GP) is returned blank (contain no clinical information) or has not been returned will Version 7 Date: 30/08/2017

only be included for analysis of secondary and exploratory objectives, where appropriate.

Consented patients will not be considered evaluable if the specialist HCP reports that the patient did not take either combination therapies. If there is evidence to suggest duplication of patients, either through inadvertent duplication between different prescribers within the same clinical setting, or if a patient was switched from one combination therapy to the other, then the records identified will be considered for inclusion on a case by case basis by the advisory committee.

Patients will be automatically withdrawn if the patient or specialist HCP provides informed written or verbal notification that they no longer wish to participate at any stage of the study.

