# Table 4.Sample sizes of evaluable patients required to estimate the
expected (true) cumulative incidence of a specified adverse event
with 95% confidence intervals of different precisions (0.2% to
5%).

#### 9.6 Data Management

#### 9.6.1 Data Processing

Specialist HCP/ GP/ patient identifiable information will be stored within a unique database. All original documents and individual correspondence from HCPs will be stored for 15 years at the DSRU, with considerable care taken to preserve patient confidentiality (see below).

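### Section 9.5 promises 0.5% within +/-0.4% from 1193 patients, but about 6 expected events give roughly 0.2% to 1.1%, and the target counts some patients whom the primary analysis excludes

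*Protocol*

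**What the plan says.** Section 9.5 bases the study size on precision alone. It wants to "choose a sample size that will yield a confidence interval of a predefined width" for the major bleeding outcomes. The planning incidence comes from clinical trial data: "over the first 12 weeks of treatment was approximately 0.5% (0.1%, 0.3% and 0.1" per cent, in the order intracranial, gastrointestinal, urogenital. The target is then 1193 patients, "in order to estimate the expected (true) cumulative incidence of primary outcomes of major bleeding events of 0.5% within +/- 0.4" per cent, with an equal number desirable in the contextual cohort.

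On the method, the section says only that "Table 4 displays the samples sizes (95% confidence intervals) across a range of expected incidences and levels of precision"; it does not name the type of interval. The caption of Table 4 gives the counting unit: "Sample sizes of evaluable patients required to estimate the" incidence. Section 9.2.2 monitors recruitment in the same unit.

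Section 9.2.5 defines that unit. Patients whose 12-week questionnaires from both specialist and GP are blank or not returned are still called evaluable, but will "only be included for analysis of secondary and exploratory objectives, where appropriate". Section 9.3.5 expects some questionnaires not to come back. No return rate is given and 1193 is not inflated.

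**The concern.** The precision statement is the only justification offered for 1193, so it should describe what the study can deliver. Two things cast doubt on it.

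First, a symmetric +/-0.4 around 0.5% implies an interval from 0.1% to 0.9%. With about 6 events, the sampling distribution is skewed and a realistic interval extends further upwards than downwards. For a major bleeding outcome, the upper side is the one that matters for safety.

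Second, the table counts evaluable patients, while the primary analysis uses evaluable patients minus those with no usable 12-week form. The study could report that it reached 1193 while the primary estimate rests on fewer.

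**Working it through.** **Inputs (sections 9.5 and 9.2.5).** p = 0.005; precision d = 0.004; 95% two-sided, z = 1.96 (two-sided is assumed, and it reproduces the table); n = 1193 per cohort. The loss from missing 12-week forms is not stated.

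**Step 1: reproduce 1193.** Wald formula: n = z² p(1-p)/d² = 1.96² x 0.005 x 0.995 / 0.004² = 1194.5. With a finite-population correction, n/(1 + (n-1)/N), and N = 1,000,000, this is 1193. The protocol does not mention such a correction; N was inferred because it also matches the other Table 4 cells checked to within 1 patient (for example 4755, 2119, 9418 and 43627). At the chosen cell it changes the answer by under 2 patients.

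**Step 2: expected events.** 1193 x 0.005 = 5.97, about 6. By site: 1193 x 0.003 = 3.6 gastrointestinal; 1193 x 0.001 = 1.2 each for intracranial and urogenital.

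**Step 3: intervals for 6/1193 = 0.503%.**

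| Method | 95% interval | Half-width (points) | Upper arm (points) |
|---|---|---|---|
| Wald | 0.10% to 0.90% | 0.40 | +0.40 |
| Wilson | 0.23% to 1.09% | 0.43 | +0.59 |
| Exact (Clopper-Pearson) | 0.19% to 1.09% | 0.45 | +0.59 |

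The exact limits are the 2.5% quantile of Beta(6, 1188) and the 97.5% quantile of Beta(7, 1187). A log-scale interval, 0.503% x exp(+/-1.96/√6), gives about 0.23% to 1.12%.

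**Step 4: behaviour over repeated samples.** Under Binomial(1193, 0.005):
- the Wald interval covers the truth 92.9% of the time;
- the exact half-width exceeds 0.4 points with probability 0.71;
- the exact upper limit lies more than 0.4 points above the estimate with probability 0.98.

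**Step 5: size needed to meet the stated precision.** At p = 0.5%, a half-width of 0.4 points needs about 1357 patients (Wilson) or 1483 (exact). An upper arm of no more than 0.4 points needs about 2140 by either method.

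**Step 6: effect of the counting unit.** At n = 1193 the Wald half-width is 1.96 x √(0.005 x 0.995/1193) = 0.400 points, so there is no slack. The losses below are assumptions; the last column is 1193/(1 - loss).

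| Assumed loss | Patients in primary analysis | Wald half-width (points) | Exact interval at 0.5% | Evaluable patients needed to leave 1193 |
|---|---|---|---|---|
| 5% | 1133 | 0.411 | 0.18% to 1.11% | 1256 |
| 10% | 1074 | 0.422 | 0.17% to 1.13% | 1326 |
| 20% | 954 | 0.448 | 0.16% to 1.19% | 1492 |
| 30% | 835 | 0.478 | 0.14% to 1.25% | 1705 |

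**The case against.** **On precision.** The Wald formula is a common planning device and 1193 follows from it. If the sentence is read as a statement about the point estimate, the estimate falls within 0.4 points of a true 0.5% with probability 94.2%, which is close to what is promised. The half-width shortfall is moderate (0.45 or 0.43 against 0.40), and the protocol never set a criterion for the upper arm alone. The size is also hedged, as ideal, desirable and to be confirmed. All of this stands and limits the severity. It does not remove the point, because section 9.5 states its criterion as the width of a confidence interval. Using a Wald interval at analysis would show 0.10% to 0.90%, but at less than nominal coverage. The SAP may name an interval method; the precision printed in the protocol would still need to agree with it.

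**On the counting unit.** Only patients with nothing usable from both sources drop out. The protocol plans reminders, GP back-up and a monthly review that includes questionnaires returned and classed as void (sections 9.3.5, 9.3.3 and 9.6.1.1). These steps may keep the loss small, but they do not change the definition of evaluable.

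**Stronger readings that the documents do not support:**
- *1193 is an arithmetic error.* It reproduces. The finite-population correction is a minor note: it is unstated and out of place when estimating a true incidence, but immaterial at the chosen cell.
- *The protocol claims to exclude risks above 0.9%.* It makes no such claim.
- *The hazard modelling is undermined by too few events.* Section 9.7.1 already makes it conditional on at least five reports.
- *Late recruits count toward 1193 but cannot contribute, because recruitment and data collection end on the same day.* Section 9.1 has the study "continue for a maximum of 36 months, or until the target sample size (1193 tbc) for both cohorts has been achieved", which does not clearly keep recruitment open for 36 months. The checklist in Annex 2 defines the end of data collection as the date when the analytical dataset is completely available. The 13 weeks run from antiplatelet start, not from recruitment, and section 12.1 allows an extension.

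**Conclusion.** The point holds on both counts and should be fixed. The stated +/-0.4 is correctly computed but is not what a suitable 95% interval delivers at about 6 events: roughly 0.2% to 1.1%, with a half-width of 0.43 to 0.45 points and an upper arm of +0.59. This rests on the protocol's own 0.5% and on treating the 12-week risk as a simple proportion with full follow-up; the planned survival analysis has to allow for censoring as well.

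The mismatch between the patients counted and the patients analysed does not depend on the interval method. Its direction is certain, since any loss takes even the Wald half-width above 0.400. Its size is unknown, because the protocol gives no return rate; the 0.42 and 0.45 points at 10% and 20% loss are illustrations.

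The primary estimate itself is unaffected and no powered test depends on 1193.

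**What to change.** Keep 1193 per cohort and make these changes:

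1. **Section 9.5:** say that about 6 events are expected at 0.5%, that the 95% interval would then be roughly 0.2% to 1.1%, and that it is an exact or Wilson interval. Use the same method in the SAP.
2. **Section 9.5 or 9.7.1:** say that the site-specific estimates (3.6, 1.2 and 1.2 expected events) are descriptive.
3. **Section 9.2.2, section 9.2.5 and the Table 4 caption:** count toward 1193 only patients with at least one non-blank 12-week questionnaire, from the specialist or the GP, and monitor recruitment in that unit.
4. **Minor:** when Table 4 is next revised, state or remove the finite-population correction.

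The cost is mainly wording. The stated precision becomes less favourable, and the target may be reached later within the existing 36-month limit. The target itself does not rise. If the sponsor would rather keep +/-0.4 as a true half-width, Step 5 shows the price: about 1357 (Wilson) or 1483 (exact) analysable patients per cohort.

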# Table 4.Sample sizes of evaluable patients required to estimate the
expected (true) cumulative incidence of a specified adverse event
with 95% confidence intervals of different precisions (0.2% to
5%).

#### 9.6 Data Management

#### 9.6.1 Data Processing

Specialist HCP/ GP/ patient identifiable information will be stored within a unique database. All original documents and individual correspondence from HCPs will be stored for 15 years at the DSRU, with considerable care taken to preserve patient confidentiality (see below).

#### 9.6.1.1 Review of data

All returned questionnaires with clinical data will be coded onto the study database. Medically important adverse events selected for follow-up will be coded as a priority. There will be a regular monthly review of both the number of patients identified and study questionnaires returned, processed, and classified as void. This will assist in determining the point at which the final cohort size will be achieved. Aggregate data will be reviewed at interim and end of study milestones.

#### 9.6.1.2 Coding of data

Data on indications, exposure, relevant medical history and medication use plus events of interest will be coded directly from targeted closed format questions on the questionnaire (which reference Medical Dictionary for Regulatory Activities (MedDRA) terminology) and coded onto the bespoke study database. Other events reported on the questionnaires as free text will be coded onto this database using the DSRU Event Dictionary Doctor Summary Term synonym list that is mapped to MedDRA, in order to enable consistent reporting to be provided using MedDRA terminology.

Study specific coding procedures will facilitate consistency in coding the data. An SOP will be created upon development of the study specific SCEM database and will be maintained within the DSRU. Regular meetings of DSRU staff will be held to discuss study questionnaires that are difficult to code. A consensus opinion will be reached by medically qualified staff.

#### 9.6.1.3 Confidentiality procedures

All DSRU staff sign confidentiality agreements and the DSRU is registered with the office of the Data Protection Registrar (Registration No. Z5438861).

DSRU information security policies are in place to preserve the confidentiality, integrity and availability of the organisation's systems and data. These include ensuring the premises provides suitable physical and environmental security, all DSRU equipment is secure and protected against malicious software, the network can only be accessed by authorised DSRU staff, telecommunication lines to the DSRU premises are protected from interception by being routed overhead or underground and personal receive training regarding security awareness.

All original documents, individual correspondence from specialist HCPs, will be stored for 15 years at the DSRU, with considerable care taken to preserve the confidentiality of data. The DSRU databases are well protected. To ensure patient anonymity, the names and addresses of patients will be deleted from the DSRU database at an appropriate time point (provisionally this is at datalock or earlier if patients have provided informed Version 7 Date: 30/08/2017

notification that they wish to withdraw from the study, but the DSRU will request an extension to this to comply with CHMP requirements). Until this time, only appointed staff would have access to such data.

#### 9.6.2 Project Advisory Committee

A Project Advisory Committee (AC) will be set up to be comprised of the study investigators and other experts. The role of the AC will be to oversee the smooth running of the project and provide scientific, statistical and technical advice when needed and will meet at regular intervals (3 to 12 monthly depending on the stage of the study, either in person or by teleconference).

The AC is broadly analogous to a Safety Monitoring Committee or Review Board, but the purpose may be slightly different in that the AC advises on the effective progress of the study. The first AC meeting will orientate the project team members and establish the logistics for specialist and patient recruitment and confirm patient inclusion criteria. Subsequent AC meetings will clarify the understanding of the ongoing project requirements, monitor progress through assessment of data within the interim reports [specialist/cohort accrual rates, preliminary analyses of individual variable responses on questionnaires], consider any additional proposed inclusion criteria, and act as a forum to review and discuss any queries.

#### 9.7 Data Analysis

The data analysis plan and study objectives will be constructively aligned to meet study aim.

#### 9.7.1 To quantify the cumulative incidence (risk and rate) of major bleeding according to the TIMI classification of non-CABG Related Bleeding (Table 1) occurring in the 12 week observation period, overall and stratified by intracranial, gastrointestinal and urogenital bleeding sites.

The following relates to Section 8.2 primary objective and relates to haemorrhage within gastrointestinal and urogenital organ sites (which meets the criteria for a TIMI major non CABG related bleed) and all intracranial sites (as defined in Table 1). This time to event analysis will be performed separately for the rivaroxaban exposed cohort and the contextual cohort, as defined according to exposure at index (date antiplatelet therapy was prescribed as part of the acute management of the ACS).

<sup>1 In the event of a change in treatment resulting in a switch in treatment group, person-time contributed will be censored at the time of switching, thus analysis will not be 'intention to treat' as this is an observational study.

For each cohort, for whom acute management of ACS applies, the numerator for this analysis will comprise of adjudicated incident major bleeding events (overall and stratified by intracranial, gastrointestinal and urogenital bleeding sites) defined according to primary objective that were reported during the 12 week observation period post index date. These adjudicated events will have been reviewed by an expert panel using all available information from SCEM questionnaires, follow-up and any additional documentation. Patients for whom events were misreported will be excluded from the analysis (events will be excluded, but denominator data will still be included); patients for whom events were misclassified will be reclassified as appropriate. In addition, for each cohort, for the three organ sites specified in the primary outcome, counts of each of the individual components of the TIMI major non CABG related bleeding criteria will be summarised. Where an individual has one or more criterion for an individual organ site of interest, counts will also be summarised – in such individuals the first report will be regarded as the incident event. Since SCEM data are right censored, the cumulative incidence (risk and rate) of the primary outcomes reported during treatment within the 12 week observation period will be calculated using survival analysis methodology.

For each individual case, relevant person-time will be estimated according to duration of observation up to event date. For each individual non-case, relevant person-time will estimated by either exit date – index date; or censor date – index date; or stop date (+ 2 days ) – index date. For each cohort separately, a semi-parametric time-dependent Cox Proportional Hazards regression model will be used to estimate the crude cumulative incidence over the 12 week observation period.

Non-parametric Kaplan-Meier plots will be presented to describe time-to event as well as smoothed estimates of the empirical hazard function to describe how the crude baseline risk of the event changes over time.

Estimates of the hazard function will also be modelled to determine whether the baseline hazard (risk) of the event increases or decreases with time. A constant hazard over time may be consistent with a background (not caused by the drug) event rate, whereas a non-constant hazard over time may be an indicator of a drug-event relationship. The null hypothesis that the hazard rate of the selected event in patients will be constant during the 12 week period following the start of treatment will be tested

<sup>1 This excludes patients prescribed rivaroxaban 2.5mg for non-ACS related indications

<sup>2 Censor date = date of loss to follow-up

<sup>3 2 days allocated to person-time to account for half-life of drug

Version 7 Date: 30/08/2017

by fitting a parametric time to event model (e.g. Weibull). Such models have a shape parameter that indicates whether the hazard is significantly increasing or decreasing over time. At least five reports of an event are deemed necessary for modelling purposes.

